#### 7. STUDY SCHEDULE

In traditional 3+3 paradigm settings, eligible volunteers will be assigned to one of the candidate dose cohorts. The starting dose of the dose escalation scheme begins from

level A.

The schedule of assessment is tabulated in front of the protocol main text. The assessments or procedures to be performed at each study visit are listed below. The results of protocol specific assessments and procedures will be recorded in the source documents for all study volunteers and on the appropriate page of the eCRF. Unscheduled visit will be arranged when investigator considers necessary. Healthy volunteers should come fasted for all scheduled visits except visit 8, and 9. The definition of "pre-dose" means the timing prior to the 1st dose of that day (level A-D), or the timing for examinations scheduled on that day (2nd and 4th days of level D). The definition of "post-dose" means the timing after the 1st dose on Day 5. The duration of dosing time between breakfast and lunch from Day 2 to Day 5 should be as close to those for Day 1. Volunteers should take Careseng 1370 for breakfast on that day. Similarly, time points for pre-dose PK blood sampling on Day 2 to Day 5 should be as close as that on Day 1.

#### Screening (Days -14 to -1; Visit 1)

- Obtain informed consent form
- Assign volunteer identifier
- Obtain medical history
- Collect volunteer demographics data
- Record medication history (including concomitant medications)
- Measure height
- Measure body weight
- Perform physical examination
- Assess vital signs
- Conduct 12-lead EKG (test performed within 14 days are acceptable)
- Perform pregnancy (urine or serum test for female volunteers of childbearing potential)
- Conduct laboratory tests (with immunology test) (test performed within 14 days are acceptable) (fasting)
- Conduct chest X-ray (test performed within 14 days are acceptable)
- Assess the volunteer's eligibility for the study (inclusion/exclusion criteria)
- Record adverse events
- Dispense diary

## 1st Hospitalization (Day -1 to Day 1; Visit 2)

#### Day -1

Registration for hospitalization in the evening

#### Day 1

#### Pre-dose (fasting)

- Measure body weight
- Perform physical examination
- Assess vital signs
- Conduct 12-lead EKG
- Pre-dose PK blood sampling
- Diary return and dispensing
- Assess the volunteer's eligibility for the study (inclusion/exclusion criteria)

#### During the treatment

- Dosing before breakfast at site
- Perform physical examination (8 hours post-first dose, ±20 minutes are allowed)
- Assess vital signs (1, 4 and 8 hours post-first dose, ±20 minutes are allowed)
- Conduct 12-lead EKG (1, 4, 8, and 12 hours post-first dose, ±20 minutes are allowed)
- Conduct laboratory tests (excluding immunology test, only for 8 hours post-first dose, ±20 minutes are allowed)
- Dosing before lunch at site (not applicable for Dose level A and D)
- Record adverse events
- Record concomitant medications

#### 1st Discharge (Day 2; Visit 3)

#### Pre-dose (fasting)

- Measure body weight
- Perform physical examination
- Assess vital signs
- Conduct 12-lead EKG
- Conduct laboratory tests (with immunology test) together with pre-dose PK blood sampling

During the treatment

- Dosing (if scheduled) before breakfast at study site

#### Post-dose

- Conduct 12-lead EKG about 1 hour after IP administration (except level D)
- Record adverse events
- Record concomitant medications
- Drug (except level A and D) dispensing, and diary return and dispensing

#### Dosing Visits (Days 3 and 4; Visits 4 and 5)

#### Pre-dose (fasting)

- Measure body weight
- Perform physical examination
- Assess vital signs
- Conduct 12-lead EKG
- Conduct laboratory tests (except immunology test) together with PK blood sampling
- Drug (except level A and D) and diary return

#### During the treatment

- Dosing (if scheduled) for breakfast at site

#### Post-dose

- Conduct 12-lead EKG about 1 hour after IP administration (except level D on Day 4)
- Record adverse events
- Record concomitant medications
- Drug (except level A and D) and diary dispensing

#### 2nd Hospitalization (Day 4 to Day 5; Visit 6)

#### Day 4

Registration for hospitalization after planned dosing (if scheduled) on Day 4

*Note: This implementation aims to perform the planned procedures at the similar timing as those on Day 1.* 

## Day 5

Pre-dose (fasting)

- Measure body weight
- Perform physical examination
- Assess vital signs

- Conduct 12-lead EKG
- Conduct laboratory tests (except immunology test) together with PK blood sampling
- Drug (except level A and D) return, and diary return and dispensing

During the treatment

- Dosing before breakfast at site (last dose for level A and D)
- Dosing before lunch at site (not applicable for Dose level A and D; last dose for level B and C)

#### Post-dose PK blood sampling

- Dose level A and D: post-dose PK blood sampling at 0.5 hour (± 5 minutes), 1 hour (± 5 minutes), 2 hours (± 5 minutes), 4 hours (± 5 minutes), 6 hours (± 5 minutes), 12 hours (± 20 minutes), 24 (± 2) hours (at Visit 7), 48 (± 2) hours (at Visit 8), and 72 (± 2) hours (at Visit 9)
- Dose level B and C: post-dose PK blood sampling at 0.5 hour (± 5 minutes), 1 hour (± 5 minutes), 2 hours (± 5 minutes), 4 hours (± 5 minutes), 4.5 hours (± 5 minutes), 5 hours (± 5 minutes), 6 hours (± 5 minutes), 7 hours (± 5 minutes), 8 hours (± 5 minutes), 9 hours (± 5 minutes), 10 hours (± 5 minutes), 12 hours (± 20 minutes), 16 hours (± 20 minutes), 24 (± 2) hours (at Visit 7), 48 (± 2) hours (at Visit 8), and 72 (± 2) hours (at Visit 9)
- Conduct laboratory tests (except immunology test) (only for 4 hours post-dose, ±20 minutes are allowed)
- Perform physical examination (only for 4 hours post-dose, ±20 minutes are allowed)
- Assess vital signs (only for 4 hours post-dose, ±20 minutes are allowed)
- Conduct 12-lead EKG (only for 1, 4, 8, and 12 hours post-dose, ±20 minutes are allowed)
- Record adverse events
- Record concomitant medications

#### 2nd Discharge (Day 6, 24 (± 2) hours post-dose; Visit 7)

- Measure body weight
- Perform physical examination
- Assess vital signs
- Conduct 12-lead EKG
- Conduct laboratory tests (with immunology test) together with PK blood sampling for 24 (± 2) hours post-dose (fasting)
- Record adverse events

- Record concomitant medications
- Diary return and dispensing

#### Follow-up Visit (Day 7, 48 (± 2) hours post-dose; Visit 8)

- PK blood sampling for 48  $(\pm 2)$  hours post-dose
- Diary return
- Record adverse events
- Record concomitant medications

#### Follow-up Visit (Day 8, 72 (± 2) hours post-dose; Visit 9)

- PK blood sampling for 72 ( $\pm$  2) hours post-dose
- Record adverse events
- Record concomitant medications

#### Follow-up Visit (Day $12 \pm 2$ ; Visit 10)

- Measure body weight
- Perform physical examination
- Assess vital signs
- Conduct 12-lead EKG
- Conduct laboratory tests (except immunology test) (fasting)
- Record adverse events
- Record concomitant medications

#### Final Visit (Day 22 ± 2; Visit 11, or within 3 days after withdrawal)

- Measure body weight
- Perform physical examination
- Assess vital signs
- Conduct 12-lead EKG
- Perform pregnancy test for female volunteers of childbearing potential
- Conduct laboratory tests (with immunology test) (fasting)
- Record adverse events
- Record concomitant medications

#### **Un-scheduled** visit

Items performed should be per investigator's decision except the following:

- Record adverse events
- Record concomitant medications

#### 8. ADVERSE EVENTS

#### 8.1 Definitions

#### - Adverse Event (AE):

An AE is any untoward medical occurrence in a volunteer or clinical investigation participant administered a study medication and that does not necessarily have a causal relationship with this treatment. An AE can therefore be any unfavorable and unintended sign, symptom, or disease temporally associated with the use of a study medication, whether or not related to the study medication. Laboratory abnormalities should not be recorded as AEs unless determined to be clinically significant by the Investigator.

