#### 1.3 **Potential Risks and Benefits**

There will be no potential benefits for healthy volunteers to participate in this study.

Potential risks of Careseng 1370 are based on the toxicology findings in Sprague-Dawley (SD) rats. Possible influence on coagulation prolonged prothrombin time (PT) and activated partial thromboplastin time (APTT) was noted in both sexes of rats receiving mid- (1,350 mg/kg/day) and high-dose (2,700 mg/kg/day) for 13 weeks. But the prolonged PT and APTT were not seen at the end of recovery period in 2,700 mg/kg recovery animals. It was also noted that the mean body weights of mid- and high-dose male rats were 9.3% and 13.8% lower than that of the controls, respectively. Final mean body weight of high-dose recovery male rats was 11.8% lower than that of the controls. Final mean body weight gains of mid- and high-dose male rats were 15.7% and 23.2% lower than that of the controls. Final mean body weight gains of high-dose recovery males was 19.2% lower than that of the controls. Therefore, body weight loss and bleeding prolonged are possible risks that subjects in this study may experience.

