#### 2. OBJECTIVES AND ENDPOINTS

#### 2.1 Objectives

#### **Primary objective:**

The primary study objective is to explore the safety and tolerability profiles of Careseng 1370 as single agent based on DLT observed in healthy volunteers. The results will be employed for future study to determine the MTD of Careseng 1370 to treat chemotherapy-induced myelosuppression in advanced non-small cell lung cancer (NSCLC) patients.

DLT is defined as any  $\geq$  Grade 2 adverse event from Day 1 to Day 10 (DLT observation period), causally at least possibly related to Careseng 1370 administration as judged by the investigator. The grading system applied in this study is "Guidance for Industry: Toxicity Grading Scale for Healthy Adult and Adolescent Volunteers Enrolled in Preventive Vaccine Clinical Trials" (Appendix 1), issued by United States Food and Drug Administration in September 2007. The definition of Grade 5 (death) was added to this grading system as it was not defined in the guidance (Section 8.2 and Appendix 1).

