#### 8.2 AE/SAE Intensity and Relationship Assignment

#### - AE/SAE Intensity

The investigator must rate the intensity for all AEs that occur during the study, following "Guidance for Industry: Toxicity Grading Scale for Healthy Adult and Adolescent Volunteers Enrolled in Preventive Vaccine Clinical Trials" (Appendix 1), issued by United States Food and Drug Administration in September 2007. The definition of Grade 5 (death) was added to this grading system as it was not defined in the guidance.

The toxicity grade of adverse events will be rated according to the following definition by the investigator when AEs are not listed in the US FDA Guidance (Appendix 1) applied in this study:

- Grade 1 (Mild): No interference with activity
- Grade 2 (Moderate):
   Some interference with activity not requiring medical intervention
- Grade 3 (Severe):
   Prevents daily activity and requires medical intervention
- Grade 4 (Life threatening):
   Emergency room visit or hospitalization
- Grade 5 (Death)

Note: The definitions of Grade 1 to Grade 4 follow "Guidance for Industry: Toxicity Grading Scale for Healthy Adult and Adolescent Volunteers Enrolled in Preventive Vaccine Clinical Trials" issued by United States Food and Drug Administration in September 2007 (Appendix 1). The definition of Grade 5 (death) was added to this grading system as it was not defined in the guidance (Section 8.2 and Appendix 1).

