#### 8.3 Collecting, Recording and Reporting of Adverse Events

8.3.1 Collecting and Reporting of AE

AEs may be volunteered spontaneously by the study volunteer, discovered as a result of general questioning by the study staff, or determined by physical examination. All AEs will be recorded on the eCRF. For all AEs, the investigator must pursue and obtain adequate information both to determine the outcome of the AE and to assess whether it meets the criteria for classification as a serious AE requiring immediate notification. Follow-up of the AE, even after the date of study drug discontinuation, is required if the AE persists. The study volunteer will be followed until the event resolves or stabilizes at a level acceptable to the investigator.

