#### Intent-to-treat (ITT) population:

- Volunteers receive any Careseng 1370

Demographic analysis, safety evaluation and pharmacokinetic analysis will be performed on the ITT population. Decision of the MTD will be made based on DLT observation of evaluable subjects.

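### Laboratory values enter the DLT count only if the unblinded investigator calls them clinically significant, so a Grade 2 or higher asymptomatic value can be left out, which biases escalation and the MTD upward

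*Protocol*

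**What the plan says.** The primary objective is to explore the "safety and tolerability profiles of Careseng 1370 as single agent based on DLT observed in healthy volunteers" (protocol section 2.1). A DLT is set at or above a "Grade 2 adverse event from Day 1 to Day 10 (DLT observation period), causally at least possibly related to Careseng 1370 administration", with relatedness judged by the investigator. Section 10.2.1 adds: "Decision of the MTD will be made based on DLT observation of evaluable subjects".

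Section 8.1 controls which laboratory findings become adverse events: "Laboratory abnormalities should not be recorded as AEs unless determined to be clinically significant by the Investigator". Clinical significance is not defined.

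Section 8.2 ties grading to adverse events: "The investigator must rate the intensity for all AEs that occur during the study". Causality assessment is likewise prescribed for adverse events. An event that Appendix 1 does not list is graded by its effect on activity, and Grade 1 is "No interference with activity". Section 8.3.1 says that events are reported spontaneously, "discovered as a result of general questioning by the study staff, or determined by physical examination"; laboratory review is not in that list.

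Section 1.3 names a laboratory finding as a preclinical risk: "Possible influence on coagulation prolonged prothrombin time (PT) and activated partial thromboplastin time (APTT) was noted in both sexes of rats". Section 4.1 states that there is no blinding.

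In the SAP, the DLT tables (14.3.1.1 and 14.3.1.4) are subsets of treatment-emergent adverse events. The continuous laboratory layout classes values as Normal, NCS or CS, without a toxicity grade. The key to clinical-relevance transitions (Instructions and Abbreviations, item 7) puts Normal to NCS under Unchanged.

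**The concern.** The DLT threshold is written as a grade. For laboratory toxicity, an ungraded judgement comes before it: a value called not clinically significant never becomes an adverse event, whatever its size. Two volunteers with the same value can then be counted differently. The person making the call knows the dose and can know how many DLTs the cohort already has.

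The escalation rule and the MTD rest on counts in cohorts of 3 to 6, so a single record matters. Healthy volunteers aged 20 to 40 may have a sizeable laboratory change without symptoms, and one of the risks the protocol names is a laboratory finding. If such findings are undercounted, the trial escalates more readily than its own grade threshold implies and may report too high an MTD. The SAP would then show a Normal to NCS change as no change in the transition table.

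**Working it through.** **No stated figure is in dispute.** The protocol gives no operating characteristics for its 3+3 rule. Its only design figure here is the maximum number of evaluable volunteers, 4 cohorts × 6 = 24, which reproduces.

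**Tracing one value through the documents.** Take an asymptomatic laboratory value in the Grade 2 or higher range, measured between Day 1 and Day 10.
1. Section 8.1: if marked NCS, it is not recorded as an adverse event.
2. Section 8.2: grading and causality apply to adverse events, so neither is required for this value.
3. Section 2.1: a DLT must be an adverse event, so it is not a DLT.
4. Sections 4 and 10.2.1: escalation and the MTD use DLTs, so it does not enter the rule.
5. SAP: it appears in the visit summaries and listings, counted as NCS, and as Unchanged if the baseline was Normal.

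No section makes a Grade 2 or higher laboratory value an adverse event or a DLT regardless of the significance call. The relevant data are collected: section 7 schedules seven laboratory panels from Day 1 to Day 6 (Day 1 at 8 hours, Days 2, 3 and 4, Day 5 pre-dose and at 4 hours, Day 6), and the hematology panel includes INR and APTT.

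**Effect of one excluded event (section 4 rule).**
- 2 of 3 becomes 1 of 3: stop becomes expand.
- 2 of 6 becomes 1 of 6: stop becomes escalate, or complete at level C.
- 1 of 3 becomes 0 of 3: at levels A and B, expand becomes escalate. At level C both results lead to expansion, so nothing changes at that step.

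**Probability of stopping.** Let p be the true probability of a qualifying DLT per volunteer, f the share kept out as NCS, c = p(1 − f) the counted rate, and q = 1 − c. Stopping means two or more counted DLTs at that level.
- Levels A and B: P(stop) = 1 − [q³ + 3cq² × q³]
- Level C, which goes to 6 after 0 or 1 of 3: P(stop) = 1 − [q⁶ + 6cq⁵]

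The documents give neither p nor f, so both are assumptions. With p = 0.33 and every DLT a laboratory finding:
- f = 0, c = 0.33, q = 0.67. A and B: 1 − [0.3008 + 0.4444 × 0.3008] = 0.566. C: 1 − [0.0905 + 0.2673] = 0.642.
- f = 0.5, c = 0.165, q = 0.835. A and B: 1 − [0.5822 + 0.3451 × 0.5822] = 0.217. C: 1 − [0.3389 + 0.4019] = 0.259.

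Range over p, from f = 0 to f = 0.5:

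| True rate p | P(stop), A and B | P(stop), C |
|---|---|---|
| 20% | 0.291 to 0.094 | 0.345 to 0.114 |
| 30% | 0.506 to 0.186 | 0.580 to 0.224 |
| 40% | 0.691 to 0.291 | 0.767 to 0.345 |
| 50% | 0.828 to 0.400 | 0.891 to 0.466 |

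With only part of the toxicity in the laboratory (10% non-laboratory and an independent 30% laboratory DLT rate), P(stop) at A and B is 0.640 if all count, 0.368 if half of the laboratory events are kept out, and 0.094 if all are. At level C it is 0.717, 0.430 and 0.114.

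**The case against.** **An investigator's significance call is a legitimate design choice.** It keeps isolated transient values from stopping a volunteer: a DLT means discontinuing drug (section 4.3) and is a withdrawal criterion (section 3.4). This stands, and it argues against simply declaring every such value a DLT. It does not explain why a threshold defined by grade is applied only after an ungraded judgement.

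**A reader might infer that the DSMB would never see these values.** The documents do not support that. They do not say what the DSMB receives. Laboratory change is a secondary endpoint, tabulated by visit and listed by subject. The supported statement is narrower: nothing requires values marked NCS to be graded for the DSMB or counted.

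**A reader might infer that a Grade 2 APTT prolongation is being hidden.** Only the title of Appendix 1 is available here, so whether it grades PT or APTT, and at what value, cannot be checked. If it does not, section 8.2 grades by interference with activity. A silent prolongation would then be Grade 1 and not a DLT even if recorded as an adverse event. That is a second route to the same gap, and removing the gate alone would not close it.

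**The rat signal should not be overstated.** It is described as possible, appeared at 1,350 and 2,700 mg/kg/day over 13 weeks, and was not seen at the end of recovery in the 2,700 mg/kg animals. Level C is 3 × 652 = 1,956 mg/day, or 32.6 mg/kg at 60 kg. With the protocol's divisor, 1,350/6.2 = 217.7 mg/kg, about 6.7 times higher; the human equivalent of the NOAEL, 108.8 mg/kg, is about 3.3 times higher. Nothing in the documents supports a 33% rate or a half share marked NCS.

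**Causality remains a judgement by the same unblinded investigator.** True: changing the first gate leaves the second. Three of the causality definitions do mention abnormal laboratory results, but they apply to events already recorded.

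**Conclusion.** The point holds. Sections 8.1, 2.1 and 8.2 together allow a laboratory value in the Grade 2 or higher range to stay outside the DLT count on the investigator's significance call alone, and the SAP adds nothing that would reveal it by grade. The direction is certain because the gate can only remove events: fewer counted DLTs, more escalation, a higher MTD.

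The size is not known. One excluded event is enough to change a decision at any of levels A to C, except that 1 of 3 against 0 of 3 makes no difference at level C. The fall in stopping probability (0.566 to 0.217 at A and B, 0.642 to 0.259 at C) rests on an assumed 33% true rate, all of it laboratory toxicity, and half of it marked NCS.

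A reader might conclude that events were in fact suppressed. The documents show only that the rule permits it. This should be corrected because the DLT count carries the primary objective and the correction is cheap.

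**What to change.** **Protocol.** Reconcile sections 2.1, 8.1 and 8.2 and the SAP transition key. State explicitly whether laboratory values meeting Grade 2 or higher on Appendix 1 enter the adverse event record and the DLT assessment regardless of the significance call. State also how PT and APTT are graded if Appendix 1 does not list them. Which rule to adopt is for the sponsor and the DSMB, since it affects who stops dosing.

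**SAP.** These steps use data already collected:
- Grade every post-dose laboratory value that Appendix 1 covers, whatever its NCS or CS class.
- Add a toxicity-grade shift table from baseline, by dose level, beside the clinical-relevance transition table.
- List values of Grade 2 or higher marked NCS from Day 1 to Day 10.
- Report a sensitivity DLT count that includes them, next to the protocol-defined count, and supply it to the DSMB for any remaining decision.

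The SAP is dated September 2022 and expected the last volunteer to leave in March 2022, so a protocol change may come too late to affect escalation. The SAP additions still let a reader judge whether the reported MTD depends on the gate.

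**Cost.** A short clarification, some extra records, one table, one listing and one additional count. The sensitivity count may include isolated transient values, so it should be labelled as such and not replace the protocol-defined count.

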#### - Expected AE:

Expected AE is defined as any event, the specificity or severity of which is consistent with the current investigator brochure or other technique documents.

#### - Unexpected AE:

Unexpected AE is defined as any event, the specificity or severity of which is not consistent with the current investigator brochure or other technique documents. "Unexpected", as used in this definition, refers to an adverse drug experience that has not been previously observed (e.g., included in the investigator brochure) rather than from the perspective of such experience not being anticipated from the pharmacological properties of the pharmaceutical product.

#### - Serious Adverse Event (SAE):

Serious Adverse Event (SAE): A Serious Adverse Event is defined as an AE meeting one of the following conditions:

- Death during the period of protocol defined surveillance
- Life Threatening Event (defined as a participant at immediate risk of death at the time of the event)
- An event requiring in volunteer hospitalization or prolongation of existing hospitalization during the period of protocol defined surveillance
- Results in congenital anomaly or birth defect
- Results in a persistent or significant disability/incapacity

Sponsor:

 Based upon appropriate medical judgment, the event may jeopardize the participant and may require medical or surgical intervention to prevent one of the outcomes listed above.

